7.2.2 Vital signs and vaccine reactions

Vital signs will be assessed before and for 30 minutes following each vaccination. Study subjects will be provided with a 28-day diary card to record vaccine reactions. Study subjects will be asked to record daily body temperature and local and systemic solicited adverse events on the day of vaccination and for the

next 6 days. Study subjects will also be asked to record unsolicited adverse events in their diary card, on the day of vaccination and for the next 27 days. Vaccine reactions will be assessed at each visit and recorded in the eCRF for the corresponding visit. If a vaccine reaction meets the criteria of an SAE, the investigator or delegates will complete and submit an SAE report form (see also section SAE reporting).

For the recording of local vaccine reactions:

- The largest diameter of redness or swelling at the injection site will be measured daily on the day of vaccination and for the next 6 days and recorded in the eCRF
- Subjects will be asked to indicate the maximum pain, tenderness and pruritus (itchiness) they experience at the injection site on a scale from 0 to 3 (0: no pain 1: Mild discomfort to touch 2: Discomfort with movement 3: Significant discomfort at rest) on the day of vaccination and for the next 6 days.

In addition, subjects will be asked to record local or general AE in the diary card that will be reviewed at each visit. AEs reported in the diary cards will be transcribed in English by the study center staff (if applicable) prior to recording in the eCRF. AEs transcribed to English from the diary card will be verified for accuracy during the site monitoring visit.

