6.1.10 Recording of adverse events

- The subjects will be instructed to contact the investigator/study center staff immediately should they manifest any signs or symptoms they perceive as significant.
- During the vaccination visits (on Study Days 0, 28, and 168), the subject will be provided 28-day diary cards. On Study Day 0 they will also be provide with a measurement device template (in mm) for measuring the largest diameter of solicited local reactions (erythema [redness], swelling), and an oral thermometer for recording daily temperature (in °C or in °F) on the day of vaccination and for the next 6 days.
- Subjects will be asked to record daily the maximum pain, tenderness and pruritus [itchiness] they
 experience at the injection site on a scale from 0 to 3 (0: no pain 1: Mild discomfort to touch 2:
 Discomfort with movement 3: Significant discomfort at rest) on the day of vaccination and for the
 next 6 days.
- The subject will record body temperature (oral) and any local/systemic AEs (i.e., on the day of vaccination and during the next 6 days) or any solicited or unsolicited AEs (i.e., on the day of vaccination and during the next 27 days occurring after injection) on the 28-day diary card. The study center will contact the subject 7 days (+/-2 days) after each vaccination to assess subject status and to remind the subject to complete the diary cards and return them at the next study visit.

• The subject will be:

- Trained on how to complete the diary.
- Requested to record their individual data in their diary cards, as described above.
- Asked to provide a telephone contact, so the study center staff can contact them for the safety follow-up 7 days (+/- 2 days) after each vaccination.
- Advised that they will be asked about the occurrence of any symptoms or events requiring medical attention (i.e., requiring a doctor or emergency room visit) and the use of concomitant medication up to Study Day 336.
- Instructed to bring their diary cards to clinic visit on Study Days 28, 56, and 196 as follows:
 the diary card provided on Study Day 0 will be collected on Study Day 28; the diary card
 provided on day 28 will be collected on Study Day 56, and the diary card provided on day
 168 will be collected on Study Day 196. The staff will review the diary cards entries with the
 subject.

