15.3 Appendix 3: FDA guidelines for grading vaccine reactions

Table 4: FDA Grading of Injection site reactions						
	Grade 1	Grade 2	Grade 3	Grade 4		
Pain (pain without touching)	Does not interfere with activity	Repeated use of non- narcotic pain reliever	Any use of narcotic pain reliever or prevents daily	Emergency room (ER) visit or hospitalization		
Tenderness (pain when area is touched)	Mild discomfort to touch	Discomfort with movement	Significant discomfort at rest	ER visit or hospitalization		
Pruritis associated with injection See also Skin: Pruritis (itching - no skin lesions)	Itching localized to injection site AND Relieved spontaneously or with< 48 hours treatment	Itching beyond the injection site but not generalized OR Itching localized to injection site requiring ≥ 48 hours treatment	causing inability to	NA		
Erythema/Redness *	2.5 – 5 cm	5.1 – 10 cm	> 10 cm	Necrosis or exfoliative dermatitis		
Induration/Swelling **	2.5 – 5 cm and does not interfere with activity	5.1 – 10 cm or interferes with activity	> 10 cm or prevents daily activity	Necrosis		

^{*}In addition to grading the measured local reaction at the greatest single diameter, the measurement should be recorded as a continuous variable.

^{**} Induration/Swelling should be evaluated and graded using the functional scale as well as the actual measurement.

Table 5: FDA Grading of vital signs abnormalities

Vital Signs *	Mild (Grade 1)	Moderate (Grade 2)	Severe (Grade 3)	Potentially Life Threatening (Grade 4)
Fever (°C) ** (°F) *	38.0 – 38.4 00.4 – 101.1	38.5 – 38.9 101.2 – 102.0	A 39.0 – 40 B 102.1 – 104	> 40 > 104
Tachycardia - beats per minute	101 – 115	116 – 130	> 130	ER visit or hospitalization for arrhythmia
Bradycardia - beats per minute***	50 – 54	45 – 49	< 45	ER visit or hospitalization for arrhythmia
Hypertension (systolic) - mm Hg	141 – 150	151 – 155	> 155	ER visit or hospitalization for malignant hypertension
Hypertension (diastolic) - mm Hg	91 – 95	96 – 100	> 100	ER visit or hospitalization for malignant hypertension
Hypotension (systolic) – mm Hg	85 – 89	80 – 84	< 80	ER visit or hospitalization for hypotensive shock
Respiratory Rate – breaths per minute	17 – 20	21 – 25	> 25	Intubation

Subject should be at rest for all vital sign measurements.

^{**} Oral temperature; no recent hot or cold beverages or smoking.

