6.3.14.2 Solicited Local, Systemic and Other Adverse Events

The following solicited local and systemic adverse events as well as solicited other adverse events will be collected. The grading of severity will be graded according to the FDA Guidance for Industry Toxicity Grading Scale for Healthy Adult and Adolescent Volunteers Enrolled in Preventive Vaccine Clinical Trials (2007) – also see protocol Appendix 3.

Solicited local adverse events:

- Redness/erythema
- Pain
- Swelling/edema
- Tenderness
- Pruritus

Injection site reactions grading				
	Grade 1	Grade 2	Grade 3	Grade 4
Pain (pain without touching)	Does not interfere with activity	Repeated use of non-narcotic pain reliever	Any use of narcotic pain reliever or prevents daily activity	Emergency room (ER) visit or hospitalization

PAREXEL International Statistical Analysis Plan

Tenderness (pain when area is touched)	Mild discomfort to touch	> 24 hours or interferes with activity Discomfort with movement	Significant discomfort at rest	ER visit or hospitalization
Pruritus associated with injection See also Skin: Pruritus (itching - no skin lesions)	Itching localized to injection site AND Relieved spontaneously or with < 48 hours treatment	Itching beyond the injection site but not generalized OR Itching localized to injection Site requiring ≥ 48 hours treatment	Generalized itching causing inability to perform usual social & functional activities	NA
Erythema/Redness*	2.5 – 5 cm	5.1 – 10 cm	> 10 cm	Necrosis or exfoliative dermatitis
Induration/Swelling**	2.5 – 5 cm and does not interfere with activity	5.1 – 10 cm or interferes with activity	> 10 cm or prevents daily activity	Necrosis

^{*}In addition to grading the measured local reaction at the greatest single diameter, the measurement should be recorded as a continuous variable.

Solicited systemic adverse events:

- Nausea/vomiting
- Diarrhea
- Headache
- Fatigue
- Myalgia

The grading of systemic adverse events will be as follows:

^{**} Induration/Swelling should be evaluated and graded using the functional scale as well as the actual measurement.

Statistical Analysis Plan

Systemic	Mild	Moderate	Severe	Potentially Life
(General)	(Grade 1)	(Grade 2)	(Grade 3)	Threatening
				(Grade 4)
Nausea/vomiting	No interference	Some	Prevents daily	ER visit or
	with activity or 1	interference with	activity, requires	hospitalization for
	- 2 episodes/24	activity or > 2	outpatient IV	hypotensive shock
	hours	episodes/24	hydration	
		hours		

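### Injection-site pain and pruritus are scored on the tenderness scale but graded on other criteria, and both schedules limit V3 to medically attended AEs although all dose-2 AEs are wanted (low severity)

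*Protocol*

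**What the plan says.** **Scoring and grading of local reactions.** Protocol 7.2.2 asks subjects for the "maximum pain, tenderness and pruritus (itchiness) they experience at the injection site on a scale from 0 to 3 (0: no pain", continuing "1: Mild discomfort to touch 2: Discomfort with movement 3: Significant discomfort at rest". Protocol 6.1.10 repeats the instruction and the anchors: "Subjects will be asked to record daily the maximum pain, tenderness and pruritus [itchiness] they" feel at the site, each day from vaccination through the following six days.

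Protocol 7.1.6.2 and 9.8.2 and SAP 6.3.14.2 send solicited reactions to the FDA table in Appendix 3, which has three separate rows. "Tenderness (pain when area is touched" is one. "Pain (pain without touching" is another; its Grade 3 is "Any use of narcotic pain reliever or prevents daily activity". The pruritus row starts at "Itching localized to injection site AND Relieved spontaneously or with< 48 hours treatment" and reaches Grade 3 at "Generalized itching causing inability to perform usual social & functional activities". Protocol 9.8.2 and SAP 6.3.14.2 tabulate each symptom by severity.

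**Unsolicited AEs after dose 2.** In the schedules of events (protocol Appendix 2 and SAP 6.1) the unsolicited-AE row carries footnote (f), medically attended events only, at V3 (Day 56). V2 and V5, where the dose-1 and dose-3 diaries are collected, carry (g), all AEs. The secondary endpoint in protocol 3.3 covers unsolicited AEs on the vaccination day and the next 27 days. Protocol 6.3.5 has AEs recorded at V3 without that limit, 7.2.1 has everything reported in the diary recorded, and SAP 6.3.14.3 summarises all AEs in the 28 days after each vaccination, naming the second.

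**The concern.** A score built on touch, movement and rest does not contain what the pain and pruritus grades need: interference with activity and reliever use for pain; spread, duration of treatment and function for itch. Without a mapping, a severity table for these symptoms may not mean what its label says. Comparing reactogenicity is a secondary objective, and protocol 1.4 names injection-site pain as the one safety difference seen with earlier formulations.

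The V3 code conflicts with the endpoint it serves. Because SAP 6.3.14.3 presents unsolicited AEs separately for vaccinations 1, 2 and 3, a site that obeyed the footnote could under-record dose 2 relative to the other two doses.

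**Working it through.** **Part 1: anchors against grades** (protocol 6.1.10 and 7.2.2; Appendix 3 Table 4; SAP 6.3.14.2). Cells are paraphrased.

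| Level | 0-3 score, all three items | Tenderness row | Pain row | Pruritus row |
|---|---|---|---|---|
| 1 | on touch | same | activity unaffected | local; clears by itself or with under 48 h of treatment |
| 2 | on movement | same | activity affected, or repeated non-narcotic reliever beyond 24 h | past the site but not general, or local with 48 h or more of treatment |
| 3 | at rest | same | narcotic reliever, or daily activity prevented | general, with loss of usual function |
| Levels matching | | 3 of 3 | 0 of 3 | 0 of 3 |

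If the score were entered as the grade, the error could run either way:
- Significant pain at rest, activity unaffected, no repeated or narcotic reliever: score 3, Grade 1 (two too high).
- Significant itch discomfort at rest, local, clearing by itself: score 3, Grade 1 (two too high).
- Pain on movement treated with a narcotic reliever: score 2, Grade 3 (one too low).

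This concerns 2 of 5 solicited local reactions, at each of 3 doses, for scores 1-3. The documents give no frequencies.

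**Part 2: days that depend on the V3 code.** Inputs:
- Dose-2 window: days 0-27 after V2, 28 days (protocol 3.3).
- All-AE telephone call: V2+5 to V2+9 (both schedules).
- V2: Day 28 (-3/+7) = Days 25-35. V3: Day 56 (-3/+7) = Days 53-63, and at least 3 weeks after V2 (protocol 6.3.2, 6.3.5).
- Laboratory sub-study visit A2: 7 days (-3/+7) after vaccination = V2+4 to V2+14 (SAP 6.1, footnote k).

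Days dependent on the code = min(27, V3 offset from V2) - day of last all-AE contact.

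| V3 held at | Last all-AE contact | Days | Share of 28 |
|---|---|---|---|
| V2+27 or later | call, day 5 | 27 - 5 = 22 | 79% |
| V2+27 or later | call, day 7 (nominal) | 27 - 7 = 20 | 71% |
| V2+27 or later | call, day 9 | 27 - 9 = 18 | 64% |
| V2+21 | call, day 5 | 21 - 5 = 16 | 57% |
| V2+21 | call, day 9 | 21 - 9 = 12 | 43% |
| V2+21 | A2, day 14 | 21 - 14 = 7 | 25% |

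V3 at V2+21 is within the rules, for example V2 on Day 35 and V3 on Day 56. The range is therefore 12-22 days. For laboratory sub-study subjects (at least 10% of enrolment) it is 7-22 days, if AEs are also taken at A2; the later of call and A2 falls between day 5 and day 14. With V3 at V2+21, days 22-27 (6 days) come after the visit whatever its code.

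The next scheduled all-AE visit is V4: nominally 168 - 56 = 112 days after V3, at shortest 161 - 63 = 98 and at longest 175 - 53 = 122. No dose-2 diary is due then. If sites follow protocol 6.3.5 and 7.2.1, 0 days depend on the footnote.

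**The case against.** **Grading.** The documents never call the 0-3 score the grade. They name the FDA table as the standard and make the investigator responsible for grading (protocol 7.2, 10.1). Several steps could supply the missing inputs:
- the scripted questions at the 7-day call (6.3.3);
- a supplemental visit to assess severity (6.3.4 and schedule footnote e);
- staff review of the diary with the subject (6.1.10);
- concomitant medication (6.1.9), which would show a narcotic reliever;
- treatment, severity and medical attention recorded per event (7.2.1).

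No passage describes collecting activity interference for injection-site pain, or the spread of itch. That silence is weak evidence, because headache, fatigue and myalgia are also graded on activity with no diary item described, and neither the diary nor the eCRF is shown. All of this stands. A reader might infer that pain and pruritus will be misgraded; the documents do not show that. What remains is that the described score does not yield the grade and no rule links the two.

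**V3.** Loss requires a site to let one footnote letter override 6.3.5 and 7.2.1, with a collected diary in hand that 6.1.10 tells staff to transcribe. V4 is also coded for all AEs. This too stands and makes the harm conditional. It does not remove the contradiction: protocol 7.2 asks for all AEs at all visits unless specified otherwise, and a site could read (f) as such a specification. A reader might also infer that every window day after the call, 18-22 days, hangs on the footnote. That holds only when V3 falls at V2+27 or later.

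**Conclusion.** Both inconsistencies are on the face of the documents; the harm from each is conditional, and the severity is low.

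1. The shared score does not give the Appendix 3 grade for pain or pruritus. Severity rows are at risk only if the score is used as the grade. Presence or absence of these symptoms, and tenderness grades, are unaffected.
2. The V3 code contradicts the endpoint, the visit text and the SAP summary rule. If followed, it exposes 12-22 of 28 days (43-79%), or 7-22 (25-79%) in the laboratory sub-study if AEs are taken at A2, for events without medical attention only. The number of events missed cannot be derived, because the documents give neither the share not medically attended nor the timing of onset.

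The affected outputs are descriptive safety tables (protocol 9.8). A reader might infer a bias between arms or an effect on the co-primary results. The documents support neither: the scale and the schedule are the same in both arms, and the co-primary endpoint is serological.

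**What to change.** **Scoring.** In protocol 6.1.10, 7.2.2 and the diary, use the separate Appendix 3 anchors for pain and for pruritus, and keep touch, movement and rest for tenderness. If diaries are already complete:
- where the grading inputs were not collected, report these two items on the scale used and do not label them FDA grades;
- where they were collected, state in protocol 7.1.6.2 and SAP 6.3.14.2 that the investigator grades from those fields and not from the 0-3 score.

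**Schedule.** Change unsolicited AEs at V3 from (f) to (g) in protocol Appendix 2 and SAP 6.1, and leave V4 as (g). This does not recover days 22-27 when V3 is held at V2+21.

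**Cost.** Revised wording for two diary items, with translation, or one sentence or table label if diaries are complete; one letter in two tables. No extra visits or procedures.

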7.2.3 Laboratory test abnormalities

In subjects participating in the clinical laboratory sub-study, abnormal laboratory test values will be recorded individually in an AE form if they qualify as AE (see Section 7.1.5) and are not part of the data supporting a medical diagnosis already reported as an AE. Any Grade 4 potentially life-threatening laboratory abnormality (see Appendix 4) within 7 days after a study injection will stop any further study vaccinations in the subject, irrespective of the study vaccine relationship, as defined in Section 7.8.

7.2.4 SAEs, Medically Significant Event and New Onset of Chronic Illness

All SAE, expected or unexpected, medically significant event or new onset of chronic illness occurring between obtaining the subject's written consent to participate in the study and the last study visit will be documented in the eCRF, first in an AE form. For SAE, upon completion of the AE form, and confirmation that the AE is an SAE, the investigator or delegates will be prompted to complete and submit a SAE report form. Follow-up SAE forms may be completed and submitted as needed e.g., if the event outcome, treatment and resolution are not known at the time of the initial report. The follow-up information should contain sufficient detail to allow for a complete medical assessment of the case and an independent determination of possible causality, such as concomitant medications, or other conditions possibly explaining the SAE if any (must be consistent with the medical history recorded at baseline), relevant diagnostic tests, and autopsy report if applicable. All copies of source data attached with the SAE report form will be de-identified to protect subjects subjects' privacy.

In addition, the reports should record: subject unique study ID, age, gender, weight, initial or follow-up report, date of the event, date of report, and individual completing the report.

7.3 Expedited reporting procedures to study sponsor and pharmacovigilance agent

7.3.1 Serious Adverse Events

SAEs require prompt or immediate reporting to the site Principal Investigator or designates. The site Principal Investigator will be responsible for reporting the SAEs to study sponsor/pharmacovigilance agent as per protocol, and to the IRB/REB if/as required by institutional policies and procedures.

The site Principal Investigator or delegates will complete and submit a SAE form in the eCRF, within 24 hours of becoming aware of the SAE. An E-mail notification of the SAE will be sent automatically to the Medical Monitor/pharmacovigilance agent appointed by study sponsor. The Medical Monitor/pharmacovigilance agent will assess the SAE report and proceed to report to the appropriate regulatory bodies as described in section 7.4.

Once additional relevant information is received, the report should be updated WITHIN 24 HOURS.

7.3.2 Reporting of pregnancy

Female subjects, if not post-menopausal or surgically sterile are required to use adequate contraception methods as part of the entry criteria.

If any study subject becomes or is found to be pregnant during the treatment period or within 4 weeks of the last injection of study vaccines, the pregnancy will be reported in the same way as SAE to study sponsor using the SAE Report Form, including an estimated date of conception (EDC), and the date of last study vaccine dose. Pregnancies will be followed by the investigator until completion of the pregnancy to learn the outcome, as congenital anomaly/birth defect is a SAE. Spontaneous abortion, ectopic pregnancy and stillbirth will also be considered as a SAE. At the end of the pregnancy, whether full-term or premature, information on the status of the mother and child will be forwarded to the study sponsor. Generally, follow-up will be no longer than 6 to 8 weeks following the estimated delivery date.

7.4 Reporting to regulatory authorities

The study sponsor will appoint a Medical Monitor/pharmacovigilance agent who will report adverse events to the appropriate regulatory authorities as outlined below.

The study sponsor or delegates will report any unexpected fatal or life-threatening suspected adverse reactions to the appropriate regulatory authorities as soon as possible but no later than 7 calendar days of initial receipt of the information.

The study sponsor is also responsible for reporting to the appropriate regulatory authorities and to all investigators no later than 15 calendar days after determining that the information qualifies for reporting, any:

- suspected adverse reaction that is both serious and unexpected, reported by any study center irrespective of the location.
- suspected adverse reaction that is both serious and unexpected occurring in any of the subjects
 of the clinical trial, which are identified by or come to the attention of the sponsor after the end
 of the clinical trial
- findings from clinical, epidemiological, or pooled analysis of multiple studies or any findings from animal or in vitro testing that suggest a significant risk in humans exposed to the drug
- clinically important increase in the rate of a serious suspected adverse reaction over that listed in the protocol or investigator brochure.

If the regulatory authority requests any additional data or information, the study sponsor or delegates must submit it as soon as possible, but no later than 15 calendar days after receiving the request.

The study sponsor or delegates will submit periodic reports of the progress of the trial, if and as, requested by the regulatory authorities.

7.5 Institutional Reporting of AEs and SAEs

The investigator will be responsible for reporting all SAEs directly to the relevant ethical review body (IRB/REB) according to institutional policies.

In addition, the investigator will be responsible for reporting AEs directly to the relevant ethical review body (IRB/REB) if and as requested by institutional policies, and will also provide the ethical review body with any safety reports prepared by/on behalf of the study sponsor.

7.6 Type and duration of follow-up of subjects after AEs

All AEs and SAEs will be followed until they are resolved (return to normal or baseline values), unless: 1) they are judged by the investigator to be no longer clinically significant, 2) the investigator attributes the AE/SAEs to a cause other than the study drug or assesses them as chronic or stable, or 3) the subject is lost-to follow-up. Supplemental measurements and/or evaluations may be necessary to fully investigate the nature and/or causality of an AE or SAE. This may include laboratory tests, diagnostic procedures or consultation with other healthcare professionals. If the subject dies, any post-mortem findings (including histopathology) must be provided to the Sponsor or designee. In addition, the designated Medical Monitor may request blood tests, diagnostic imaging studies or specialist physician consultations in order to further evaluate any AE or abnormality considered to be potentially clinically significant.

Any clinically significant abnormalities persisting at the end of the study will be followed by the investigator until resolution or until a clinically stable endpoint is reached.

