4.3 Subject withdrawal

Subjects who are withdrawn because of SAEs/AEs must be clearly distinguished from subjects who are withdrawn for other reasons. Investigators will follow subjects who are withdrawn as result of a SAE/AE until resolution or stabilization of the event and will assess, record, and report AEs and SAEs as instructed in Section 7 (ASSESSMENT OF SAFETY).

Withdrawals for any reasons will not be replaced.

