- Advised on how to contact study center staff. Subjects will be advised to immediately contact the investigator (or his/her designee) in the event of a SAE or change inhealth.
- Informed to notify their health care professional(s) (e.g., primary care physician) that they are participating in a clinical research study of HBV vaccine.

- Be informed of the appointments (date and time) for the next planned visits to the study center (Study Days 28, 56, 168, 196, and 336). At select sites, subjects will also be required to come for 3 additional visits one week after each vaccination (Study Days 7, 35 and 175) to provide a blood sample for the clinical laboratory sub-study.
- Any unreturned diary cards will be sought from the subject through telephone call(s) or any other convenient procedure.

Diary cards will be available in all official languages of participating countries. The investigator/study center staff will transcribe the collected information into the eCRF in English. AEs from the diary card transcribed to English from another language will be verified for accuracy during the site monitoring visit.

Diary cards are considered source documents.

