6.3.7 End of study visit

The end of study visit will be performed on Study Day 336 (+/-14 days) or earlier in case of withdrawal.

- Physical/History-directed physical examination.
- Blood samples for measurement of anti-HBs, anti pre-S1, and anti pre-S2 levels and characteristics will be taken.
- SAE, AE requiring medical attention and the use of concomitant medications will be recorded in the eCRF
- In case of withdrawal: reason for withdrawal will be documented in the eCRF
- Subject will be advised that the study center staff may need to contact them in case new information, such as lack of seroprotection (anti-HBs levels <10 mIU/mL), becomes available.

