7.1.7 Assessment of the outcomes

The investigator will assess the outcome of all AEs (including SAEs) recorded during the study as:

- Ongoing
- Recovered/resolved to pre-immunization health status
- Recovered/Resolved with sequelae
- Recovering/Improving
- Stabilized
- Unknown/Lost to Follow-up
- Fatal (SAE)

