7.2 Methods and timing for assessing, and recording safety parameters

Unless specified otherwise all AE occurring between obtaining the subject's written consent to participate in the study and subject's last study visit will be documented in the eCRF at all visits. All AE data and clinical laboratory data will be included in the study report.

Clinical investigators and ultimately the Site Principal Investigator have the primary responsibility for AE identification, documentation, grading, assignment of attribution and reporting to the sponsor.

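### Protocol 7.6 lets the investigator's attribution to another cause, by itself, end the duty to follow an active SAE in a subject who stays on study

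*Protocol*

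**What the plan says.** Protocol 7.6 starts from a general duty to follow AEs and SAEs until they resolve, then lists three exceptions:

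1. The investigator judges the event no longer clinically significant.
2. "the investigator attributes the AE/SAEs to a cause other than the study drug", or the investigator considers the event chronic or stable.
3. The subject is lost to follow-up.

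Two other provisions set a follow-up duty without regard to cause:

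- Protocol 4.3: "Investigators will follow subjects who are withdrawn as result of a SAE/AE until resolution or stabilization of the event".
- Protocol 7.6, last paragraph: "Any clinically significant abnormalities persisting at the end of the study will be followed by the investigator until resolution", or until the condition is clinically stable.

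Protocol 7.2.4 deals with follow-up information on SAEs of any cause: "Follow-up SAE forms may be completed and submitted as needed". It gives as an example an outcome or resolution not yet known at the first report. It also says that the follow-up information should allow a full medical assessment and an independent view of causality.

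**The concern.** Follow-up of an SAE serves the subject's care, and it also lets others check the first causality judgement. A rule that stops the duty once the investigator names another cause lets that first judgement end the search for information that might revise it. Protocol 7.1.8 asks both the investigator and the sponsor to assess causality, but the exception in 7.6 depends on the investigator alone.

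At stake are the follow-up that a subject with an active SAE is owed, and the completeness of the safety record. For such an event the outcome could stay recorded as ongoing or unknown, with no duty on the site to find out more.

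**Working it through.** No arithmetic applies. The check is a clause-by-clause reading of 7.6, followed by a search of both documents for text that would restore the duty.

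**What attribution alone adds.** Exception 1 already releases events that are no longer clinically significant. The second half of exception 2 already releases chronic or stable ones. For subjects still in contact with the site, the only further events that attribution releases are those still clinically significant and neither chronic nor stable. The clause names SAEs and sets no limit on severity.

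**Which of those events another rule covers.**

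| Active SAE judged unrelated | Rule that applies | Duty to follow? |
|---|---|---|
| Subject withdrawn because of it | 4.3, no condition on cause | Yes |
| Clinically significant abnormality still present at the end of the study | 7.6, last paragraph, no condition on cause | Yes |
| Subject stays on study, from attribution to the end of the study | None found | No |

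**Provisions that come near the third row.**

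- 7.2: AEs "will be documented in the eCRF at all visits", up to the last study visit. This secures recording at visits, not follow-up to resolution.
- 7.1.7: "The investigator will assess the outcome of all AEs (including SAEs) recorded during the study". Ongoing and unknown are permitted entries, so the form can be completed without following the event further.
- 6.1.10: "Subjects will be advised to immediately contact the investigator (or his/her designee) in the event of a SAE". This puts the first step on the subject.
- 7.2.4: follow-up SAE information is expected, but the forms are permissive and no duration is set.
- 7.3.1: an SAE report is updated within 24 hours once new information arrives. Nobody is required to seek it.
- 7.6: the Medical Monitor may ask for tests or consultations, at discretion.
- Schedule of events (Protocol Appendix 2): SAE collection is marked as continuous, which concerns capture. The footnote that calls for follow-up to resolution concerns reactions to the vaccine.
- 7.8 and 7.9: a life-threatening event within 7 days of an injection stops further doses whatever its cause, and the DMC then meets. No length of follow-up is set.
- 6.1.2: eligibility for vaccination and for continued participation is verified before each dose. This protects against a further dose during an active SAE, but it is a check on dosing days only.

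The SAP sets no follow-up rule for these events.

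**Effect on the analysis.** SAP 6.3.14.3 summarizes and lists SAEs whatever their attributed cause, and plans no table of AE outcomes. No planned summary changes.

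**The case against.** The best case for leaving the text alone has four parts.

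- **The protections are substantial.** SAEs are captured and reported whatever their cause. The sponsor assesses causality too (7.1.8), and the Medical Monitor or pharmacovigilance agent assesses each SAE report (7.3.1). Section 7.2.4 foresees follow-up reports when the outcome is not yet known, with no limit by cause. Eligibility is re-verified before each dose, and no dose follows Day 168. All of this stands and keeps the effect small. None of it obliges the site to follow the event.
- **There is no firm contradiction.** A reader might infer that 7.6 conflicts outright with 4.3 and with its own last paragraph. The documents do not support that. Both are specific, unqualified rules that fit beside a general rule with exceptions, and they are best read as prevailing. The protocol does not state the order, so saying so would help, but this is clarification and not repair of a conflict.
- **Time between visits does not measure the gap.** A reader might size the problem by the long stretches of the schedule without a visit or call. Those stretches are the same for an SAE judged related, because 7.6 sets no contact frequency for any event. They show visit spacing, not the effect of the exception.
- **The exception lifts a duty but does not forbid follow-up.** This is true. A careful site would probably continue, and the documents do not show that any site would stop.

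**Conclusion.** The point holds in a narrow form. Exception 2 in 7.6 removes the duty to follow an active, clinically significant and unstable SAE once the investigator attributes it to another cause. No other provision restores the duty while the subject stays on study.

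The effect on patient safety and on the safety record is small. Its frequency cannot be estimated, since the documents give no rate of such SAEs. Sample size, power, type I error and the planned analyses are unaffected. A reader might also infer that unrelated SAEs go unrecorded, or that one arm is favored. The documents support neither: capture and reporting do not depend on cause, and the plan blinds the staff who assess outcomes.

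The conclusion rests on two readings. The first is that 4.3 and the last paragraph of 7.6 prevail over the exception. The second is that the abnormalities meant in that last paragraph include SAEs that are still active; the protocol does not define the term. If either reading fails, the gap is wider.

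This is a cheap improvement, not a flaw that threatens the trial's conclusions.

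**What to change.** In Protocol 7.6, limit attribution as a stand-alone exception to non-serious AEs that did not lead to withdrawal. Add one sentence, for example: SAEs of any attributed cause, and AEs leading to withdrawal as in Section 4.3, are followed to resolution or stabilization, and the last paragraph of this section applies whatever the attributed cause.

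This extends to all SAEs a standard that 4.3 already uses. The other exceptions, for loss to follow-up and for events that are chronic, stable or no longer clinically significant, can stay. The cost is a few more follow-up entries for SAEs judged unrelated, limited because follow-up may still stop at stabilization. It needs no extra scheduled visit and no change to the SAP.
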